13.8 Other aspects of clinical quality assurance, as appropriate

Not applicable.

14 Amendments to the CIP

Any amendments to the CIP shall be approved by the Chief Investigator and the Sponsor and authorised bodies as appropriate. Amendment number / updated version number etc, will be recorded on all documentation.

15 Deviations from clinical investigation plan

15.1 Statement specifying that the investigator is not allowed to deviate from the CIP, except as specified in 5.6.4 c).

Deviations from the protocol, which are found to frequently recur, are not acceptable and will require immediate action by the sponsor. Frequent non-compliances could potentially be classified as a serious breach.

15.2 Procedures for recording, reporting, and analysing CIP deviations.

Accidental protocol deviations can happen at any time. They must be adequately documented on the relevant forms and reported to the Chief Investigator and Sponsor immediately.

15.3 Notification requirements and time frames.

As above

15.4 Corrective and preventive actions and principal investigator disqualification criteria.

See compliance.

16 Device accountability

16.1 Description of the procedures for the accountability of investigational devices as specified in 7.9;

The authorised Research Team Member will keep records documenting the following:

- name of person who received, used, and returned the device;
- the date of receipt, identification, and quantity of each investigational device (batch number/serial number or unique code);
- the date or dates of use; subject identification; date on which the investigational device was returned from subject,
- the date of return of unused or malfunctioning investigational devices, if applicable;
- 16.2 Procedures and particular materials and instructions for the safe return of investigational devices, including those that are potentially hazardous.

The device will be returned to the Research Team during an in person session at the end of the 12 week trial period.

17 Statements of compliance

17.1 Statement specifying that the clinical investigation shall be conducted in accordance with the ethical principles that have their origin in the Declaration of Helsinki

The study will be conducted in accordance with the principles of the good clinical practice GCP. A favourable ethical opinion will be obtained from the appropriate Research Ethics Committee and local NHS R&D (Research & Development) prior to commencement of the study.

The sponsor will ensure that the trial protocol, patient information sheet, consent form, GP letter and submitted supporting documents have been approved by the appropriate regulatory body, Health Research Authority (HRA), main research ethics committee (REC) and that local permission has been obtained prior to any subject recruitment.

All substantial amendments and non-substantial amendments (as determined by the sponsor) will not be implemented until HRA/REC have provided the relevant authorisations. The NHS R&D departments will also be informed of any substantial amendments and non-substantial amendments. Relevant approvals must be obtained before any substantial amendment and non-substantial amendments may be implemented at sites.

All correspondence with the HRA and the REC will be retained in the Trial Master File and the Investigator Site File (maintained by the site).

Within 90 days after the end of the research project, the CI/Sponsor will ensure that the HRA and the main REC are notified that the trial has finished. If the trial is terminated prematurely, those reports will be made within 15 days after the end of the trial.

The CI will supply the Sponsor with a summary report of the clinical trial, which will then be submitted to the main REC within 1 year after the end of the trial.

The project will be conducted in accordance with the recommendations for physicians involved in research on human participants adopted by the 18th World Medical Assembly, Helsinki 1964 as revised and recognised by governing laws and EU Directives; and the principles of GCP and in accordance with all applicable regulatory requirements including but not limited to the UK Policy Framework for Health & Social Care Research.

17.2 Statement specifying compliance with this document and any regional or national regulations, as appropriate.

This document has been compiled in accordance with ISO 14155:2020

17.3 Statement specifying that the clinical investigation shall not begin until the required approval/favourable opinion from the EC and regulatory authority have been obtained, if appropriate.

The clinical investigation will not begin until approval from MHRA has been obtained.

17.4 Statement specifying that any additional requirements imposed by the EC or regulatory authority shall be followed, if appropriate.

Any additional requirements imposed by the MHRA will be followed as appropriate.

17.5 Statement specifying the type of insurance that shall be provided for subjects, if appropriate.

The sponsor of the trial is University Hospital Southampton NHS Foundation Trust. For NHS sponsored research HSG (96) 48 reference no.2 refers. If there is negligent harm during the clinical trial when the NHS body owes a duty of care to the person harmed, NHS Indemnity covers NHS staff, medical academic staff with honorary contracts, and those conducting the trial. NHS Indemnity does not offer no-fault compensation and is unable to agree in advance to pay compensation for non-negligent harm. Ex-gratia payments may be considered in the case of a claim.

17.6 Statement addressing the financing of the clinical investigation including a description of the agreement between the sponsor and investigation site(s), and where applicable with the investigator(s) if not addressed in a separate agreement.

This research project is being funded by the Medical Research Council (MRC) Funder Number: MR/W029421/1. A High Level Agreement exists between the University of Southampton and University Hospital Southampton NHS Foundation Trust.

18 Informed consent process

18.1 Description of the general process for obtaining informed consent, including the process for providing subjects with new information and process for incentives for subjects, as needed.

No data will be collected from patients before consent has been obtained. The patient will be provided with a Participant Information Sheet in person or by email. A member of the research team will explain the study to the patient either in person or by telephone or video call, providing all the relevant information and allowing the patient to ask questions. After allowing the patient enough time for them to feel that they have been able to read the form and consider the study appropriately, with time to discuss with any next of kin if they wish, the researcher will answer any additional questions and obtain written consent.

18.2 Description of the informed consent process in circumstances where the subject is unable to give it; in the case of emergency treatment, the items specified in 5.8.3.4 shall be included.

Subjects who are unable to give informed consent will not be included in the study.

19 Adverse events, adverse device effects, and device deficiencies

19.1 Definitions of adverse events and adverse device effects.

See table below

19.2 Definition of device deficiencies.

See table below

19.3 Definitions of serious adverse events including serious health threat and serious adverse device effects and, where appropriate, unanticipated serious adverse device effects.

The terms and definitions presented below are covered by the ISO standard 14155:2020 "Clinical investigation for medical devices for human subjects: good clinical practice"

Investigational	Medical device being assessed for safety or performance in a clinical investigation.
medical device	This includes medical devices already on the market that are being evaluated for new intended uses, new populations, new materials or design changes.
Adverse Event (AE)	Any untoward medical occurrence, unintended disease or injury or any untoward clinical signs (including an abnormal laboratory finding) in subjects, users or other persons whether or not related to the investigational medical device.
	This definition includes events related to:
	 the investigational device or the comparator. the procedures involved.
	For users or other persons, this definition is restricted to events related to investigational medical devices.
Serious	Adverse event that:
Adverse Event (SAE)	a) led to a death, injury or permanent impairment to a body structure or a body function.
(OAL)	b) led to a serious deterioration in health of the subject, that either resulted in:
	- a life-threatening illness or injury, or
	- a permanent impairment of a body structure or a body function, or
	- in-patient hospitalization or prolongation of existing hospitalization, or
	- in medical or surgical intervention to prevent life threatening illness
	c) led to foetal distress, foetal death or a congenital abnormality or birth defect.
	Planned hospitalization for pre-existing condition, or a procedure required by the Clinical Investigation Plan, without a serious deterioration in health, is not considered a serious adverse event.
Adverse Device	Adverse event related to the use of an investigational medical device.
Effect (ADE)	NOTE 1- This includes any adverse event resulting from insufficiencies or inadequacies in the instructions for use, the deployment, the implantation, the installation, the operation, or any malfunction of the investigational medical device.
	NOTE 2- This includes any event that is a result of a use error or intentional abnormal use of the investigational medical device.

Serious Adverse Device Effect (SADE)	Adverse device effect that has resulted in any of the consequences characteristic of a serious adverse event.
Device deficiency	Inadequacy of an investigational medical device related to its identity, quality, durability, reliability, safety or performance. This may include malfunctions, use error, or inadequacy in the information supplied by the manufacturer.
Unanticipated Serious	Serious adverse device effect which by its nature, incidence, severity or outcome has not been identified in the current version of the risk analysis report.
Adverse Device Effect (USADE)	NOTE: Anticipated SADE (ASADE): an effect which by its nature, incidence, severity or outcome has been previously identified in the risk analysis report

19.4 List of non-reportable adverse events, if applicable, including rationale.

Not applicable

19.5 Time period in which the principal investigator shall report all adverse events and device deficiencies to the sponsor and, where appropriate, to ECs and the regulatory authority.

Upon being made aware of a SADE/USADE, the CI will notify the Sponsor ([contact]) and the CRO (www.pharmexcel-cro.com) within 24 hours, with subsequent notification of the MHRA and REC within 15 days of completion of the SADE report.

19.6 Details of the process for reporting adverse events.

Any adverse event reported by participants or observed by the investigators involved in the study will be screened by the Research Team in the first instance. If the report is deemed an adverse event (e.g. user error), it will be recorded using an adverse events form which will be sent to the Monitor (PHARMExcel) who will adjudicate and USADEs will be reported to the MHRA and the sponsor. All staff will be GCP trained. A data monitoring committee will provide overall oversight.

When an unacceptable risk to participants' health and safety is identified the medical device will be recalled following the below procedure:

- 1. Participant communication: If a device fault poses an unacceptable risk, participants will receive communication explaining the recall reason. They will also be provided with a contact person (usually the project PI or clinical lead) to address any concerns or discuss the matter.
- 2. Return process: Participants will receive a postal address to return the faulty device and postage costs will be reimbursed.
- 3. Analysis and Documentation: The returned devices will undergo analysis, and the findings will be thoroughly documented.
- 4. Stakeholder engagement: Depending on the reason to recall the device, relevant stakeholders (such as material suppliers or PCB manufacturers) will be informed of the findings. A mitigation plan will be devised and implemented.
- 5. Further investigation will occur to identify the root cause of the issue, and corrective actions will be taken to prevent similar problems in the future.

The CI or Sponsor may take urgent safety measures to ensure the safety and protection of trial participants from any immediate hazard to their health and safety. The measures may be taken without prior authorisation from the MHRA or REC. However, the CI will ensure all relevant parties (Sponsor, REC and MHRA) are notified of the changes within 3 days in writing detailing the reasons for the urgent safety measures and the plan for further action.

19.7 Details of the process for reporting device deficiencies.

Any device deficiencies observed by participants should be reported immediately to a member of the Research Team – contact details are included in IFU and on device labels.

19.8 List of foreseeable adverse events and anticipated adverse device effects, together with their likely incidence, mitigation, or treatment.

Some skin irritation is a foreseeable adverse event. Use of the device should be stopped for 24 hours in the first instance to allow for recovery. If a serious irritation arises, use of the device should be discontinued. No treatment is prescribed, but a topical lotion can be applied as appropriate. There are no other anticipated adverse device effects.

19.9 Emergency contact details for reporting serious adverse events and serious adverse device effects.

Emergency contact details are included in IFU.

19.10 Information regarding the DMC, if established.

A Data Monitoring Committee will be convened.

20 Suspension or premature termination of the clinical investigation

20.1 Criteria and arrangements for suspension or premature termination of the whole clinical investigation or of the clinical investigation in one or more investigation sites.

The only criteria for suspension or premature termination of the whole clinical investigation would be a major fault arising in all the devices allocated to participants. This is not anticipated, but should such a thing occur all devices would be recalled from participants and the trial would be suspended in the first instance to enable assessment / remedy of any such fault.

20.2 Criteria for access to and breaking the blinding/masking code in the case of suspension or premature termination of the clinical investigation, if the clinical investigation involves a blinding/masking technique.

The study statistician will create the randomisation schedule and a member of the Research Team will hold a copy in case of a need to break the blinding.

20.3 Requirements for subject follow-up and continued care.

After the completion of the 12 weeks study there will be no further subject follow-up or continued care.

21 Publication policy

21.1 Statement that the clinical investigation will be registered in a publicly accessible database (see 5.4).

In accordance with the Declaration of Helsinki, a description of the clinical investigation shall be registered in a publicly accessible database before the start of recruitment activities and the content shall be updated throughout the conduct of the clinical investigation and the results, available publicly, entered at completion of the clinical investigation.

21.2 Statement indicating that the results of the clinical investigation will be made publicly available.

As above, and participants will have the option to request a summary of the results on publication.

21.3 Statement indicating the conditions and timeframes under which the results of the clinical investigation will be offered for publication including the role of the sponsor and criteria for authorship.

After full analysis of the results of the clinical investigation the data will be published in peer reviewed manuscripts authored by the Principal, co-investigators and research staff in appropriate scientific journals. The role of the sponsor, funder and affiliated institutions shall be acknowledged in all such publications.

Amendment Number	CIP version number	Date issued	Author(s) of changes	Details of changes made
	1.8	December 2024	[name]	All previous versions checked and incorporated.

22 Bibliography

- 1. Musculoskeletal Health: A 5 year strategic framework for prevention across the lifecourse, Public Health England, 2019.

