4.2 The manufacturer of the investigational device

The University of Southampton (UoS) is the legal manufacturer of the investigational device and will take on responsibility for the device itself. The project team has developed a comprehensive Quality Management System (QMS) with dedicated support from IMed, a specialist regulatory consultancy company. The device will be manufactured at UoS following the QMS to ensure device safety, function, usability, and regulatory compliance. UoS will receive parts/components from approved suppliers (e.g. Conductive Transfers Ltd for printing the conductive lamination film used in electrode manufacturing, PCBway Ltd for PCB manufacturing and population for the TENS electronic control unit) who have a demonstrated capability in manufacturing the required parts of the investigational device. For example, Conductive Transfers Ltd has supplied conductive lamination film for a medical device company (e.g. Atlantic Therapeutics) who sell an electrotherapy device for strengthening pelvic floor muscles. The electrode garment will be manufactured in the lab at UoS and the TENS electronic control unit will be assembled at UoS. Device testing will be conducted at UoS to ensure quality and the safety and functional requirements, and the requirement set in the standards (e.g. IEC 60601-1).

4.3 Model Name/number including software version and accessories, permitting full identification

Each garment will have a unique serial number. Similarly, the electronic control unit will have a unique serial number (Issue1-Electronics-001 incremented for each electronic circuit. The research team will keep a record of the electronic units and garments assigned to each participant to maintain traceability of the medical device during and after the clinical investigation. Software version is Issue 1 for the RCT and is identical for all participants.

Device constituent parts:

Garment = Issue 1; Stimulator Electronics = Issue 1; Software = Issue 1.0.0

Detachable components:

Interconnecting cable model reference: Lot1-CG-Cable

Accessories:

- USB Charging cable Model: MinTENS-RCT1-USB
- Instructions for use Model: MinTENS-RCT1-IFU
- Conductive electrode gel: MinTENS-RCT1-Gel
- Plastic Bag Model: MinTENS-RCT1-Bag

4.4 How traceability shall be achieved during and after the clinical investigation, for example, by assignment of lot numbers, batch numbers, or serial numbers.

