9.5 Point of randomisation

In person visit when the device is allocated.

9.6 Total expected duration of the clinical investigation.

12 weeks. Rolling recruitment over 5 month period, garment fabrication and fitting, 12 weeks home use, return of device. Total for study as a whole 9 months.

10 Study Procedures

10.1 Description of all the clinical investigation-related procedures that subjects undergo during the clinical investigation including any deviation from normal clinical practice.

A screening clinic visit will take place after an initial phone eligibility check to ensure that all participants have been diagnosed with knee OA according to the American College of Rheumatology criteria [13].

People who screen positive and consent to be part of the trial will be asked to attend three visits in person, complete follow-up questionnaires, and will receive a maximum of 4 phone calls over a period of approximately 3 months. The visits in person will take place in facilities within the University of Southampton, either at Winchester School of Art or Southampton General Hospital, on a mutually convenient date (daytime or exceptionally in the evenings).

In the first in person visit, a research nurse will take body measurements and will ask participants to try the standard size of TENS garment, which is closest to their measured size. After that, when the garment is ready, participants will visit the lab at Winchester School of Art to collect a garment with instructions and will receive guidance on what they need to do at home. They will be instructed to use the garment at least 5 out of the 7 days for 12 consecutive weeks. People will choose whether they prefer to undergo daily TENS in one session of 30 to 60 minutes or two separate sessions with a duration of 30 minutes each.. Participants will be given either an intervention or sham device – only the member of the research team distributing the garment at this point will be aware of which has been assigned.

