10.7 Recommended follow-up for the subjects after the clinical investigation has been completed

Not applicable

10.8 Final disposition or potential future use of samples obtained from subjects, if applicable.

Not applicable

11 Monitoring plan

This study will be monitored by PHARMExcel and may be subject to monitoring and audit by University Hospital Southampton NHS Foundation Trust, under their remit as sponsor and other regulatory bodies to ensure adherence to ICH GCP, UK Policy Framework for Health and Social Care Research, applicable contracts/agreements and national regulations. All study related documents will be made available on request for monitoring and audit by UHS, the relevant REC or other licensing bodies. A CRO, PHARMExcel will monitor the clinical study.

12 Statistical Design and analysis

12.1 Analysis population (e.g. intention-to-treat, per-protocol, as-treated) and procedures that take into account all the data.

Analysis will be on the intention-to-treat population. Levels of missing data will be monitored and we will consider whether data are missing not at random. Multiple imputation methods will be considered if <10% of the primary outcome data are missing (at random).

12.2 Descriptive statistics of baseline data, treatments, safety data and where applicable, primary and secondary endpoints.

Descriptive statistics of baseline clinical data will be presented by treatment arm (ITT).

Clinical data analysis: Pain score, motor function, safety and quality of life data will be summarised and will be reported according to CONSORT: extension to pilot and feasibility trials guidelines.

Changes in clinical outcomes from baseline will be summarised within treatment (ITT)

Process and feasibility outcomes such as recruitment and retention rate will be presented with 95% confidence intervals; adverse events (safety data) will be presented by treatment arm.

12.3 Analytical procedures including measures of precision such as confidence intervals, if applicable.

Changes in clinical scores from baseline will be summarized within treatment arm with 95% confidence intervals.

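### Section 19.6 has the Research Team judge non-serious reports before an adverse-event form exists, without excluding members who know the allocation or keeping a record of what is rejected

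*Protocol*

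**What the plan says.** Section 19.6 sets the order of events. Reports from participants and observations by investigators "will be screened by the Research Team in the first instance. If the report is deemed an adverse event", then "it will be recorded using an adverse events form which will be sent to the Monitor (PHARMExcel) who will adjudicate". The form, and with it the Monitor's adjudication, therefore follows a judgement by the Research Team. The section gives user error as an example but no criterion for the judgement.

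The definition in 19.3 is wide: it covers untoward occurrences "whether or not related to the investigational medical device". Section 19.4, headed "List of non-reportable adverse events, if applicable, including rationale", is answered as not applicable.

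On who screens, section 3 says that the research team developed the garment, and 4.2 says "The University of Southampton (UoS) is the legal manufacturer of the investigational device". The trial is described as double-blind (8.1), but 10.1 says that "only the member of the research team distributing the garment at this point will be aware of which has been assigned", and 20.2 adds that "a member of the Research Team will hold a copy in case of a need to break the blinding". These may or may not be the same person.

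On use of the data, 12.2 states that "adverse events (safety data) will be presented by treatment arm", and 8.3 lists adverse reactions among the secondary outcomes.

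**The concern.** In a masked trial, what counts as an event should be settled without knowledge of the arm, or at least leave a trace that can be checked. Here the decision comes before the record. It is made by a team with a stake in the device, and part of that team can know the allocation. If screening differs between arms, the by-arm comparison is biased. If it is the same in both arms, both rates are understated.

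The one foreseeable harm, skin irritation (19.8), is the kind of report where judgement matters, and 6.6 tells participants who have it to contact the team. Section 7.4 also makes the absence of adverse events an example of what suitability for home use means, so the team that developed the device decides which reports count against one of its own hypotheses. A report that never reached a form cannot be restored at analysis, so this belongs in 19.6 rather than in a statistical analysis plan.

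**Working it through.** The protocol gives no adverse-event rate and no screening rate, so there is no figure to reproduce. The check is a reading of the passages, followed by a scale calculation on assumed values.

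**Passages side by side**

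1. *Definition against filter.* Under 19.3 and 19.4 almost any untoward occurrence qualifies and nothing is listed as exempt. Little should remain to be screened out, yet 19.6 makes the form conditional on a screen.
2. *Who may screen.* Section 19.6 names the Research Team as a whole. Sections 10.1 and 20.2 place knowledge of the allocation with one or two of its members. No section bars them from screening, and none says that they do it.
3. *Trace.* No log of rejected reports is required in 19.6 or elsewhere in section 19.
4. *Other routes.* Section 19.5 has the Chief Investigator notify the sponsor and the CRO of serious adverse device effects within 24 hours of becoming aware. Table 1 (10.5) collects adverse effects at weeks 1, 4, 8 and 12, and the questionnaires are double-entered at the MRC LEC (13.1) and passed to the statistician (8.4).
5. *Source of the table.* Section 12.2 does not say whether the by-arm table is built from forms or questionnaires, and no section requires the two to be reconciled.

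Items 1 to 3 establish the gap. Items 4 and 5 limit it: a non-serious report made between questionnaires, screened out and not repeated on a questionnaire leaves neither an adverse-event form nor a questionnaire entry.

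**Scale (illustration only)**

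With 40 per arm (12.5.6), one affected participant lost from the count changes an arm's rate by 1/40 = 2.5 percentage points.

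Assume that 30% report an event in each arm: 0.30 × 40 = 12 against 12. If a share f of active-arm reports is screened out and none in the sham arm, the tabled ratio is 12(1 − f)/12 = 1 − f.

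| f (active arm only) | Tabled counts | Ratio, true value 1.0 |
|---|---|---|
| 10% | 10.8 vs 12 | 0.90 |
| 25% | 9 vs 12 | 0.75 |
| 50% | 6 vs 12 | 0.50 |

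With an assumed true 30% against 15% (12 vs 6, ratio 2.0), the same three shares give 10.8/6 = 1.8, 9/6 = 1.5 and 6/6 = 1.0.

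If the same share is dropped in both arms, the ratio does not change, but both rates fall; at f = 25%, 30% becomes 9/40 = 22.5%.

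These figures also assume that the table rests on the forms alone. Neither the rates nor f can be taken from the protocol.

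**The case against.** The strongest reply is that the gap is narrow. Section 10.1 says that only the distributing member is aware of the assignment, so on the protocol's own account most possible screeners are masked, and masked screening would tend to drop reports equally in both arms. The wide definition in 19.3, and the fact that even user error qualifies in 19.6, can be read as binding the screener to a low threshold. The questionnaires bypass the screen. The Monitor works throughout the study (13.1), and study documents are open to monitoring and audit (section 11). Section 7.1 disclaims verification of safety.

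Much of this stands, and it rules out three stronger readings that a reader might infer:

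- *That an unmasked person filters the events.* The text leaves this possible but does not state it.
- *That the Monitor sees nothing until the team has filtered.* Serious device effects go to the CRO separately under 19.5.
- *That the by-arm table must pass through the screen, or that losses could never be found.* The source of the table is not stated, and a screened-out report that also appears on a questionnaire would show up if forms and questionnaires were compared.

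The tie to the manufacturer also needs care. The team's membership is not defined, the sponsor is an NHS Trust, and a research nurse takes part. That the team developed the device is stated; that it belongs to the manufacturer is an inference.

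The reply does not explain why a screen is needed before recording when the definition leaves so little to exclude, and it does not cover unscheduled reports. The disclaimer in 7.1 does not remove adverse reactions from the outcomes in 8.3 or the table in 12.2.

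**Conclusion.** The point holds in limited form and is a cheap improvement, not a defect that undermines the trial. Section 19.6 puts judgement before recording for non-serious reports, does not keep members who know the allocation out of that judgement, and leaves no trace of rejected reports. The exposure is mainly to unscheduled reports not repeated on a questionnaire.

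Whether any bias arises depends on who screens, how many reports are rejected, whether rejection differs by arm, and which source feeds the table. The protocol settles none of these, so neither the size nor the direction of a bias can be estimated. A halved active-arm rate, as in the last row of the table, would need half of the active-arm reports dropped and none in the sham arm; nothing in the protocol suggests that this is expected.

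**What to change.** Amend 19.6 in three respects.

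1. Log every participant report or observation on the adverse-event form as received, before any judgement, and forward every form to the Monitor.
2. Before the Monitor adjudicates, have event status judged by an existing investigator who does not distribute devices and has no access to the randomisation schedule. The protocol does not define the team, so the sponsor should confirm that such a person is available.
3. State, with a matching line in 12.2, that the by-arm table uses these forms reconciled with the adverse-effects entries on the questionnaires.

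The cost is a wording change and a few extra short forms, some of them later classed as not adverse events.
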